#### **Serious Adverse Event Reporting (SAE)**

A serious adverse event is – any adverse drug experience occurring at any dose that results in any of the following outcomes:

- Death
- A life-threatening adverse drug experience – any adverse experience

that places the patient, in the view of the initial reporter, at immediate risk of death from the adverse experience as it occurred. It does not include an adverse experience that, had it occurred in a more severe form, might have caused death.

- Inpatient hospitalization or prolongation of existing hospitalization
- A persistent or significant disability/incapacity – a substantial disruption of a person's ability to conduct normal life functions.
- A congenital anomaly/birth defect.

Important medical events that may not result in death, be life-threatening, or require hospitalization may be considered a serious adverse drug experience when, based upon appropriate medical judgment, they may jeopardize the patient or subject and may require medical or surgical intervention to prevent one of the outcomes listed in this definition. Examples of such medical events include allergic bronchospasm requiring intensive treatment in an emergency room or at home, blood dyscrasias or convulsions that do not result in inpatient hospitalization, or the development of drug dependency or drug abuse (21 CFR 312.32).

- Important medical events as defined above, may also be considered serious adverse events. Any important medical event can and should be reported as an SAE if deemed appropriate by the Principal Investigator or the IND Sponsor, the Investigational New Drug (IND) Office.
- All events occurring during the conduct of a protocol and meeting the definition of a SAE must be reported to the IRB in accordance with the timeframes and procedures outlined in "University of Texas M. D. Anderson Cancer Center Institutional Review Board Policy on Reporting Serious Adverse Events". Unless stated otherwise in the protocol, all SAEs, expected or unexpected, must be reported to the IND office, regardless of attribution (within 5 working days of knowledge of the event).
- All life-threatening or fatal events, expected or unexpected, and regardless of attribution to the study drug, must have a written report submitted within 24 hours (next working day) of knowledge of the event to the Safety Project Manager in the IND Office. -
- The MDACC "Internal SAE Report Form for Prompt Reporting" will be used for reporting to the IND Office.
- Serious adverse events will be captured from the time the patient signs consent until 30 days after the last dose of drug. Serious adverse events must be followed until clinical recovery is complete and laboratory tests have returned to baseline, progression of the event has stabilized, or there has been acceptable resolution of the event.
- A research nurse will document information regarding the adverse event into the patient's/donor's medical record. The Study Chair will review and sign the documentation.
- Additionally, any serious adverse events that occur after the 30 day time period that are related to the study

treatment must be reported to the IND Office. This may include the development of a secondary malignancy.

#### **Reporting to FDA:**

· Serious adverse events will be forwarded to FDA by the IND Sponsor (Safety Project Manager IND Office) according to 21 CFR 312.32.

It is the responsibility of the Study Chair and the research team to ensure serious adverse events are reported according to the Code of Federal Regulations, Good Clinical Practices, the protocol guidelines, the sponsor's guidelines, and Institutional Review Board policy.

## **8.0 Criteria for Response**

1. The primary clinical endpoints for this study are anti-myeloma response to donor lymphocyte infusions and GVHD.
2. CRITERIA FOR RESPONSE: Consensus EBMT/IBMTR Response Criteria for Myeloma are to be used. Appendix E.(37)
3. Acute and Chronic GVHD will be graded according to Appendix F. Patients who develop any form of GVHD may be treated according to standard care or any extant protocol.
4. RELAPSE/PROGRESSION will be recorded by the day of detection.
5. SURVIVAL will be recorded by the day and cause of death, and measured from the date of DLI.

## **9.0 Criteria for Removal from the Study**

1. Patient/Donor withdrawal of informed consent
2. Patient death
3. Disease progression requiring anti-myeloma therapy
4. Patient/ Donor not being compliant
5. 5 years post donor lymphocyte infusion
6. If the recipient does not meet the "pre-vaccine" criteria in Section 7.0 B., the recipient and donor will be taken off the study.
7. Donor lymphocyte collection failure
8. An increasing or unexpected pattern of toxicity observed deemed unacceptable by the study chairman
9. Investigator judgment when the well being and best interest of the patient is compromised.
10. Inability of donor to provide lymphocytes after study registration

## **10.0 Statistical Considerations**

**Preliminaries.** This is a single-arm feasibility trial of Id Specific vaccinated DLI for treatment of multiple myeloma patients post allograft from a matched sibling donor who are not in CR or relapsing after transplant at least 3 months after stem cell transplant. The last myeloma therapy must be at least 3 weeks prior to entry. Labeling time of DLI as week 0, each donor will be vaccinated at weeks -8, -6, -2 and each patient will be vaccinated at weeks, 0, 4, and 8. Toxicity (TOX) will be defined as the event that the patient suffers grade 2, 3 or 4 GVHD or death within 6 months post DLI. The historical rate of TOX is 50% (54/107). The primary aim is to determine whether transfer of myeloma specific immunity is enhanced by vaccinating donors prior to donor lymphocyte infusion with an id-specific vaccine.

**Trial Conduct.** A maximum of 10 patients will be treated.

**Analysis of Myeloma Specific CTLs over time.** A generalized linear mixed model (Diggle, et al., 1998) will be fit to the longitudinal measurements of myeloma specific CTLs. For patient  $j = 1, \dots, 20$  at observation time  $t = -8, -6, -2, 0, 4, 8, 12$ , denote the myeloma specific CTL count by  $Y_{j,t}$  and covariate vector by  $Z_j$ . The model is given by

$$g\{E(Y_{j,t})\} = m + f_j(t) + b Z_j + \text{error}$$

where  $g$  is a suitable link function,  $m$  is the overall mean,  $f_j$  is a patient-specific function of  $t =$  time from day of DLI, accounting for the manner in which  $Y$  varies over time and includes a patient effect to account for correlation among the successive observations on each patient,  $Z_j$  is a component accounting for patient covariates with  $b$  is a covariate parameter vector, and "error" is the usual measurement of error.

Additional analyses of the final data will include analysis of survival times as functions of the treatments and patient prognostic covariates using an appropriate survival regression model determined by goodness-of-fit analyses.

**Toxicity Monitoring Rule.** For the purpose of safety monitoring, "toxicity" will be defined as Grade 2-4 acute GVHD within 6 months of DLI. Based on an historical toxicity rate of 50%, denoting  $q = \text{Pr}(\text{toxicity})$ , it will be assumed that  $q$  follows a beta(.50, .50) prior. The trial will be stopped early for safety if  $\text{Pr}(Q > .50 | \text{data}) > .90$ . This rule will stop the trial early if  $[\# \text{ toxicities}] / [\# \text{ patients}]$  is greater than or equal to 2/2, 3/3, 4/4, 5/6, 6/7, or 7/9. The operating characteristics of this rule are as follows:

True Pr(Toxicity)	Pr(Stop Early)	Median Sample Size
.50	.35	10
.60	.52	8
.70	.70	5
.80	.88	2

**PROTOCOL COMPLIANCE** Patients will be reviewed by the study investigators who will score the patient for toxicity, and GVHD. Data must be entered in PDMS and the Study Chairman will be the final arbiter of toxicity and other outcomes should a difference of opinion exist.

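### Section 10.0 defines toxicity in two ways against one unsourced 50% rate, and the safety rule as written counts a death without grade 2-4 acute GVHD as toxicity-free

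*Combined protocol and SAP*

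**What the plan says.** Both definitions are in Section 10.0, Statistical Considerations.

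- **Preliminaries.** TOX is "the event that the patient suffers grade 2, 3 or 4 GVHD or death within 6 months post DLI". The same paragraph adds "The historical rate of TOX is 50% (54/107"). The name TOX is not used again.
- **Toxicity Monitoring Rule.** "For the purpose of safety monitoring", toxicity "will be defined as Grade 2-4 acute GVHD within 6 months of DLI". The rule is introduced with "Based on an historical toxicity rate of 50"%. It places a beta(.50, .50) prior on the toxicity probability q and stops the trial if the posterior probability that q exceeds .50 is above .90. The boundaries are counts of toxicities over patients: 2/2, 3/3, 4/4, 5/6, 6/7, 7/9. The operating characteristics are indexed by "True Pr(Toxicity").
- **Protocol Compliance.** In a dispute, "the Study Chairman will be the final arbiter of toxicity and other outcomes". No counting rule for deaths is given.

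Section 8.0 says "Acute and Chronic GVHD will be graded according to Appendix F". It also has the day and cause of death recorded, with survival measured from DLI.

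**The concern.** The two events share a 6-month window and a rate, but not their content. The first includes death and says GVHD without qualification. The second leaves out death and says acute GVHD. A composite event cannot be rarer than one of its components, so one 50% can describe both only if the extra outcomes add essentially nothing.

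This is the trial's only numeric safety rule, and at most 10 patients are treated, so the classification of one patient can decide whether the trial stops. Under the rule as written, an outcome that the same section calls toxicity counts towards continuing.

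**Working it through.** **1. The plan's own figures.** Inputs from Section 10.0: beta(.5, .5) prior, limit .50, cutoff .90, maximum 10 patients. I assume a check after every patient, with each 6-month status known before the next patient enters. After x toxicities in n patients the posterior is beta(.5 + x, .5 + n − x). The smallest counts with Pr(q > .50) > .90 are 2/2, 3/3, 4/4, 4/5, 5/6, 6/7, 6/8 and 7/9. Under these, a trial can first stop only at 2/2, 4/5 or 6/8, so for a true rate p

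Pr(stop early) = p² + 2p⁴(1 − p) + 7p⁶(1 − p)².

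At p = .50 this is .25 + .0625 + .0273 = .340.

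| True rate | Criterion | Printed list alone | Plan's table |
|---|---|---|---|
| .50 | .340 | .299 | .35 |
| .60 | .516 | .463 | .52 |
| .70 | .708 | .658 | .70 |
| .80 | .877 | .847 | .88 |

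The posterior criterion reproduces the plan's table to within about .01. The printed list does not: it omits 4/5 (posterior .912) and 6/8 (.923), which both meet the criterion.

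**2. The same patients under the two events.** One of the first two patients has grade 2-4 acute GVHD. The other dies within 6 months without it.

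| Event counted | Count | Posterior | Pr(q > .50) | Action |
|---|---|---|---|---|
| Acute GVHD only (monitoring rule) | 1/2 | beta(1.5, 1.5) | .500 | continue |
| GVHD or death (TOX) | 2/2 | beta(2.5, .5) | .924 | stop |

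2/2 is on the printed list, so this result does not depend on the omitted boundaries.

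**3. Where 50% could come from.** 54/107 = 50.5%. Table 2 in Section 2.0 lists GVHD of grade 2 or above after DLI and has no column for death.

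- Three largest series: 27 × .56 + 25 × .48 + 54 × .46 = 15.12 + 12.00 + 24.84 = 51.96 of 106 (49.0%).
- All four series: adding 11 × .50 = 5.50 gives 57.46 of 117 (49.1%).

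No subset of the four sample sizes adds to 107. The closeness to 50% makes a GVHD-only origin plausible but does not prove it.

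**4. Sensitivity illustration only.** The documents give no rate of death without grade 2-4 acute GVHD, so I assume d = 5, 10 or 20 percentage points. The figures use the posterior criterion and the timing assumption in step 1. Every treated patient is counted; none is dropped as non-evaluable or replaced. With acute GVHD rate a, the step 1 formula uses p = a if such deaths count as toxicity-free, and p = a + d if they count as toxicity.

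| What .50 describes | d | Death toxicity-free | Death a toxicity |
|---|---|---|---|
| Acute GVHD (a = .50) | .05 / .10 / .20 | .34 / .34 / .34 | .42 / .52 / .71 |
| The composite (a = .45 / .40 / .30) | .05 / .10 / .20 | .27 / .20 / .10 | .34 / .34 / .34 |

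**The case against.** The best defence is that the narrower event is deliberate. The monitoring paragraph opens with "For the purpose of safety monitoring" and gives its own definition. Watching acute GVHD alone is a legitimate design choice, and Table 2 suggests that the 50% may be a GVHD rate. On that view the monitoring rule is coherent and the loose wording is in the Preliminaries. The GVHD difference may also be only apparent: Table 1 grades only its acute column, so grades 2 to 4 in the Preliminaries may mean acute GVHD, leaving death as the only difference. Safety oversight does not rest on the rule alone. Section 7.0 requires a written report of any fatal event within 24 hours (next working day), and Section 9.0 lets the study chairman act on a pattern of toxicity.

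Much of this stands, and it rules out three stronger readings that a reader might infer.

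- *That the plan leaves open how such a death is counted, or that the patient may be non-evaluable.* The literal rule settles the count: a treated patient without the monitored event is a patient without toxicity. Nothing in the plan sets an evaluability exclusion for the rule.
- *That 50% is shown to be wrong for acute GVHD.* It is not. It is unsourced, and the plan attaches it to both events.
- *That deaths go unmonitored.* They are reported and can be acted on.

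The defence does not remove the conflict. The fraction 54/107 is attached in the text only to the wider event, TOX has no stated use, and no sentence says that the narrowing is intended.

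**Conclusion.** The point holds as an unreconciled conflict inside the only numeric stopping rule, and should be fixed. Its size is shown by the two-patient example: .500 (continue) against .924 (stop) for the same outcomes. That result needs only the plan's prior and cutoff. How often the conflict would matter cannot be estimated from the documents, because they give no death rate. The early-stopping figures for assumed death rates show direction and sensitivity, not a likely effect, and the composite row applies only if 54/107 includes deaths.

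A reader might also infer that the printed boundaries can stay as they are provided the reference rate stays at .50. They cannot be relied on either way, because the list already departs from the stated criterion at that rate.

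**What to change.** - State one event for the safety rule: acute or any GVHD, with or without death. Make the Preliminaries and the Toxicity Monitoring Rule agree.
- If the narrower event is deliberate, say so, say that a death without grade 2-4 acute GVHD counts as toxicity-free in the rule, and say what TOX is used for.
- Give the source of 54/107, say whether it includes deaths, and tie the reference rate to the chosen event.
- Check the boundary list against the > .90 criterion whichever event is chosen, starting with 4/5 and 6/8. Recompute the boundaries and operating characteristics if the reference rate changes.

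The cost is one or two sentences, a source and a short calculation. Counting deaths needs no new data, since Section 8.0 already records them. The downside is that counting deaths against an unchanged GVHD-only 50% makes early stopping more likely: .34 becomes .42, .52 or .71 under the assumed 5, 10 or 20 points. Setting the limit to the chosen event's rate offsets this. With limit and true rate both .55, .60 or .70, the same recursion gives .38, .27 or .24.

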If the recipient does not meet the above "pre-vaccine" criteria, the recipient and donor will be taken off the study. The donor will have follow-up tests and procedures performed, as described in Section 7.0.

- 6.5 On day 0 (day of lymphocyte collection) donors will undergo a steady state pheresis to obtain lymphocytes. Donor target cell dose will be to  $\geq 2 \times 10^7$  CD3+ cells /kg recipient weight. If the target dose is not reached after 3 collections, then the donor and the recipient will be taken off the study and the apheresis product will be discarded.
  - 6.6 If successful collection, on day 0:  $1 \times 10^7$  CD3+/cells per kg will be infused into the recipient. The rest of the cells will be cryopreserved in  $5 \times 10^7$  CD3+ cells /kg recipient weight aliquot. Premedication will include only acetaminophen 650 mg po (orally) and benadryl 25 mg iv once.
- NO STEROIDS ARE TO BE GIVEN PRIOR TO LYMPHOCYTE INFUSION.
- 6.7 After DLI on same day, recipient will receive id-KLH vaccine. The vaccine will be also administered on week 4 and week 8 post DLI. The recipient will receive a total of 3 vaccines.
  - 6.8 For the donor the time of active treatment will begin the day of the first vaccine and finish 30 days after donor lymphocyte collection.
  - 6.9 For the recipient the time of active treatment will begin the day of the donor lymphocyte infusion and finish 30 days after the last vaccination.
  - 6.10 Recipients will receive GM-CSF 250 mcg/m^2 (rounded up to the nearest vial) S.C.daily for four days (days 0-3) after each vaccine. All GM-CSF injections will be given in close proximity to the vaccination, as close to the exact site of injection as possible to ensure optimal recruitment of dendritic cells. The first dose of GM-CSF will be given by a nurse, and the remaining three doses will be given by the recipient. Research staff will provide educational instructions regarding subcutaneous injection administration.
  - 6.11 Donors and/or recipients: Fever and chills associated with vaccine administration and/or GM-CSF will be treated with acetaminophen and/or meperidine. The use of non-steroidal anti-inflammatory drugs and/or steroids should be avoided.
  - 6.12 Recipients should not receive steroid premeds, or high dose steroids for other indications unless approved by the Study Chair or his designee.

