  - 6.13 Recipients failing to respond 6 months after the last vaccination can receive up to 3 subsequent doses of  $5 \times 10^7$  CD3+ cells/kg of the remaining cryopreserved cells, if no active GVHD is present. The additional lymphocyte infusions and follow up will be exactly like the first infusion.

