**E. Evaluation of Toxicity and Data Collection (Donors and Recipients)**

The severity of the adverse events observed in the proposed treatment will be graded according to the Common Terminology Criteria v3.0 (CTCAE).

Events not included in the CTCAE chart will be scored as follow:

General grading:

Grade 1: Mild: discomfort present with no disruption of daily activity, no treatment required beyond prophylaxis.

Grade 2: Moderated: discomfort present with some disruption of daily activity, require treatment.

Grade 3: Severe: discomfort that interrupts normal daily activity, no responding to first line treatment.

Grade 4: Life Threatening: discomfort that represents immediate risk of death.

Expected adverse events (AEs) related to the vaccine injection :

1. Local reactions (erythema, induration, swelling and tenderness),
2. Fever, chills,
3. Rash,
4. Myalgias and arthralgias.
5. Mild elevations in creatinine phosphokinase (CPK).

Expected adverse events (AEs) related to GM-CSF:

1. Fever, chills, diaphoresis
2. Myalgias, fatigue, malaise
3. Headache, dizziness
4. Dyspnea, bronchospasm, pleural effusion
5. Anorexia, indigestion, nausea, vomiting, diarrhea

6. Urticaria, rash, pruritus, hypersensitivity reactions
7. Bone pain
8. Thromboembolic events, phlebitis
9. Hypotension
10. Peripheral edema
11. Leukocytosis, thrombocytosis or thrombocytopenia
12. Hepatic enzyme abnormalities and bilirubin elevation have been recorded.

Expected adverse events (AEs) related to the vaccine:

1. Autoimmune reactions (hypogammaglobulinemia, collagen vascular diseases, cytopenias).
2. Local reactions

Expected adverse events (AEs) related to the DLI:

1. Graft versus host disease

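### GVHD after the repeat infusions allowed by section 6.13 does not enter the only numerical stopping rule, because the rule's 6-month window has closed before a repeat can be given

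*Combined protocol and SAP*

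**What the plan says.** Section 10.0, Toxicity Monitoring Rule: toxicity "will be defined as Grade 2-4 acute GVHD within 6 months of DLI". The trial stops if the posterior probability that the rate exceeds .50 is above .90 under a beta(.50, .50) prior. The boundaries are toxicities over patients, with at most 10 patients treated.

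Section 10.0, Preliminaries, fixes the clock: "Labeling time of DLI as week 0, each donor will be vaccinated at weeks" -8, -6 and -2, with recipient vaccines at weeks 0, 4 and 8.

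Treatment Plan:
- 6.6: the first infusion is 1 × 10^7 CD3+ cells/kg.
- 6.7: "The vaccine will be also administered on week 4 and week 8 post DLI".
- 6.9: the recipient's active treatment runs from the infusion and will "finish 30 days after the last vaccination".
- 6.13: "Recipients failing to respond 6 months after the last vaccination can receive up to 3 subsequent doses of" 5 × 10^7 CD3+ cells/kg, provided no GVHD is active. It adds: "The additional lymphocyte infusions and follow up will be exactly like the first infusion".

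GVHD is the only item under "Expected adverse events (AEs) related to the DLI" in section 7.0 E. It is secondary objective 2.2 and one of the two primary clinical endpoints in section 8.0.

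**The concern.** The rule and the repeat-dose provision run on clocks that do not overlap. The rule's clock starts at the first infusion. The repeat-dose clock starts at the last vaccination, which comes later, and both run for 6 months. The larger doses therefore fall after the period in which the rule counts GVHD.

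What is at stake is recipient safety. The plan itself treats a repeat as a GVHD hazard, since 6.13 withholds it while GVHD is active. Yet if the first few retreated patients all developed significant acute GVHD, nothing numerical would tell the team to withhold repeats from the next patient.

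**Working it through.** **1. The plan's own figures.** Taking the posterior criterion after each patient up to 10, with one outcome per patient, exact enumeration gives:

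| True rate | Printed Pr(stop) | Recomputed |
|---|---|---|
| .50 | .35 | .340 |
| .60 | .52 | .516 |
| .70 | .70 | .708 |
| .80 | .88 | .877 |

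The median sample sizes (10, 8, 5, 2) also agree. So the rule was evaluated with each patient scored once. These results need the boundaries 4/5 (posterior .912) and 6/8 (.923), which the printed list omits. The printed list alone gives .299, .463, .658 and .847. That is a separate matter, but it affects which boundaries to use in the fix.

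**2. Timeline**, taking 6 months as 26 weeks:
- Window closes: 0 + 26 = week 26.
- Earliest repeat, all vaccines given: 8 + 26 = week 34, a gap of 8 weeks.
- Vaccination ended after week 4: 4 + 26 = week 30.
- Vaccination ended after week 0: 0 + 26 = week 26, as the window closes.
- Active treatment ends: 8 + 30/7 = week 12.3.
- First long-term visit after week 34 (12 months after the last vaccine, section 7.0 D): 8 + 52 = week 60.

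**3. Dose and yield.** Each repeat is 5/1 = 5 times the first dose. One repeat needs 1 + 5 = 6 × 10^7 CD3+ cells/kg collected, and three need 1 + 15 = 16 × 10^7. The collection target in 6.5 is at least 2 × 10^7, so a donor who only just meets it leaves too little for one repeat.

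**4. The same criterion applied to retreated patients alone.** Posterior Pr(q > .50) is .818 at 1/1 (no stop), .924 at 2/2, .967 at 3/3, .985 at 4/4 and .912 at 4/5. The remaining boundaries are 5/6, 6/7, 6/8, 7/9 and 8/10. Outcomes are assumed to become known one patient at a time.
- 2 to 4 retreated: crossing requires the first two to be toxic, so the probability is q². The boundaries 3/3 and 4/4 add nothing.
- 5 retreated: q² + 2q⁴(1 − q). The second term is 4/5 with the one non-toxic patient in first or second place. At q = .50: .25 + 2(.0625)(.50) = .3125. At .70: .49 + 2(.2401)(.30) = .634. At .80: .64 + 2(.4096)(.20) = .804.
- 10 retreated: the enumeration in step 1.

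| Retreated | q = .50 | q = .70 | q = .80 |
|---|---|---|---|
| 0 or 1 | 0 | 0 | 0 |
| 2 to 4 | .25 | .49 | .64 |
| 5 | .31 | .63 | .80 |
| 10 | .34 | .71 | .88 |

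Under the rule as read here, repeat-infusion events contribute nothing to stopping at any true rate.

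**The case against.** **The window may restart.** The rule says DLI, not first DLI, and 6.13 says that infusions and follow-up repeat the first course. This is the best counter-argument, and it shows that the text can be read two ways. But the 6.13 sentence concerns infusions and assessments. It does not say that the rule's window reopens, or how a second event in the same patient enters a count of toxicities over patients. Section 10.0 ties DLI to a single week 0.

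**Other safeguards exist.** Section 7.0 B requires a GVHD assessment within 10 days before lymphocyte infusion, and 6.13 bars repeats while GVHD is active. Treatment-related serious events are reportable after 30 days. Section 9.0 allows removal for "An increasing or unexpected pattern of toxicity observed deemed unacceptable by the study chairman". A reader might infer that retreated patients are unprotected, and these provisions show that they are not. What stands is narrower: the checks act patient by patient or by judgement, and none sets a limit across patients.

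**Few may be retreated.** This stands. A reader might infer that most of a recipient's cells will be given outside the window. That presumes a collection of 16 × 10^7/kg, eight times the target. Nor can the Table 2 response rates cap the number at about half: they come from other series, and the table does not state doses. By response alone the number is 0 to 10. Yield, active GVHD and removal for progression then lower it.

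**The repeat dose may be no worse.** A reader might infer that a five-fold dose means more GVHD. The documents give no dose relationship, so this cannot be claimed. It cannot be excluded either.

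**Limiting the rule to the first infusion is a design choice.** In a 10-patient feasibility trial that is defensible if stated, but the plan does not state it.

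**Conclusion.** The gap holds. On the reading that section 10.0 supports, the window closes at about week 26. Repeat infusions at five times the first dose begin at about week 34 as planned, and never before about week 26. GVHD after a repeat would be recorded if looked for, but would not count towards stopping.

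This rests on reading DLI in the rule as the week-0 infusion, and on 6 months being about 26 weeks. Early end of vaccination shortens the gap but does not bring a repeat inside the window.

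It is a gap in safety monitoring that is cheap to close. A reader might take it for a calculation error, but the printed operating characteristics reproduce and no figure is wrong on this account. The number of patients affected cannot be given from the documents and could be zero.

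**What to change.** In section 10.0:
1. State that the existing rule refers to the first infusion, and leave it unchanged.
2. Open a new 6-month window for grade 2 to 4 acute GVHD at each 6.13 infusion. Score each retreated patient once, and count each event when it occurs. The last part matters because 6.13 sets no spacing between repeats.
3. Apply the beta(.50, .50) prior and the .90 threshold to retreated patients alone. Suspend further 6.13 infusions at 2/2, 3/3, 4/4, 4/5, 5/6, 6/7, 6/8, 7/9 or 8/10.

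The cost is a few sentences, with no added patients or apheresis. If 6.13 does not already require them, GVHD checks at about 4 and 8 weeks after each repeat are needed: first-course checks follow the vaccine visits, and the next scheduled visit could be as late as week 60.

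The downside is wrongly suspending repeats. At a true rate of .50 this happens 25% of the time with 2 to 4 retreated, 31% with 5 and at most 34% with up to 10. The plan already accepts .35 for the main rule. The added rule is also weak in small numbers: at a true rate of .70 it triggers 49% of the time with 2 to 4 retreated and 63% with 5, and it cannot act with one.

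### The printed safety-stopping list omits 4/5 and 6/8, which the protocol's own Bayesian criterion requires, and it does not deliver the tabulated operating characteristics

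*Combined protocol and SAP*

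**What the plan says.** Section 10.0, Toxicity Monitoring Rule, monitors grade 2-4 acute GVHD in the 6 months after DLI against a historical rate of 50%. The toxicity probability q "follows a beta(.50, .50) prior". The decision criterion comes first: "The trial will be stopped early for safety if" the posterior probability that q exceeds .50 is above .90. The next sentence restates this rule as counts, stopping when the ratio of toxicities to patients "is greater than or equal to 2/2, 3/3, 4/4, 5/6, 6/7, or 7/9". It gives no boundary for 5 or for 8 patients.

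A table described as the operating characteristics of this rule follows. At true toxicity rates .50, .60, .70 and .80 it gives early-stopping probabilities of .35, .52, .70 and .88, and under "Median Sample Size" the values 10, 8, 5 and 2. The Trial Conduct paragraph sets the cap: "A maximum of 10 patients will be treated". Nothing says that a look is skipped after the fifth or the eighth patient.

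**The concern.** The criterion, the list and the table are presented as one rule, so they should agree. Two signs suggest that they do not. First, the list jumps from 4 patients to 6 and from 7 to 9. Second, the table reports median sample sizes of 5 and 8, although the list contains no stop at either number.

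The list is the only form of the rule that can be applied without evaluating a beta integral, so it is likely to be what is used in practice. If it is incomplete, four cases of grade 2-4 acute GVHD in five recipients would lead to a sixth patient although the criterion has been met. The stated stopping probabilities and sample sizes would also not be those of the trial as run.

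**Working it through.** **Inputs**, all from Section 10.0: beta(.5,.5) prior; reference rate .50; stop if the posterior probability is above .90; maximum 10 patients. The calculation assumes a look after each patient with that patient's outcome known.

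**Step 1: posterior probabilities.** With x toxicities in n patients the posterior is beta(.5 + x, .5 + n − x), and Pr(q > .50 | x, n) = 1 − F(.50), where F is its distribution function.

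| x/n | Pr(q > .50) | Meets > .90 | On the list |
|---|---|---|---|
| 2/2 | .924 | yes | yes |
| 3/3 | .967 | yes | yes |
| 3/4 | .840 | no | no |
| 4/4 | .985 | yes | yes |
| **4/5** | **.912** | **yes** | **no** |
| 4/6 | .791 | no | no |
| 5/6 | .953 | yes | yes |
| 5/7 | .872 | no | no |
| 6/7 | .975 | yes | yes |
| **6/8** | **.923** | **yes** | **no** |
| 6/9 | .841 | no | no |
| 7/9 | .955 | yes | yes |

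Every listed point is a correct boundary for its own n. The error is the two omissions.

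**Step 2: where each version can first stop.** Under the full criterion, 3/3 and 4/4 must pass through 2/2. Reaching 5/6 requires an earlier 4/5 or 5/5, reaching 6/7 requires 5/6 or 6/6, and reaching 7/9 requires 6/8 or 7/8. So the criterion can first be met only at 2/2, 4/5 or 6/8. By the same reasoning the printed list can first stop only at 2/2, 5/6 or 7/9. After the second patient, each stop in the list comes one patient later than the criterion requires.

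**Step 3: early-stopping probability.** Count the paths that reach each point without an earlier stop.

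- Criterion, 4/5: the one non-toxicity is patient 1 or 2, giving 2 paths.
- Criterion, 6/8: both non-toxicities are among patients 1-5 and at least one is patient 1 or 2, giving 10 − 3 = 7 paths.
- List, 5/6: the one non-toxicity is patient 1 or 2, giving 2 paths.
- List, 7/9: both non-toxicities are among patients 1-6 and at least one is patient 1 or 2, giving 15 − 6 = 9 paths.

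Hence

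- Criterion: Pr(stop) = q² + 2q⁴(1−q) + 7q⁶(1−q)²
- List: Pr(stop) = q² + 2q⁵(1−q) + 9q⁷(1−q)²

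For example, at q = .60 the criterion gives .360 + .104 + .052 = .516 and the list gives .360 + .062 + .040 = .463.

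| True rate | Table: Pr(stop), median N | Criterion: Pr(stop), median N, mean N | Printed list: Pr(stop), median N, mean N |
|---|---|---|---|
| .50 | .35, 10 | .340, 10, 7.63 | .299, 10, 7.86 |
| .60 | .52, 8 | .516, 8, 6.50 | .463, 10, 6.83 |
| .70 | .70, 5 | .708, 5, 5.21 | .658, 6, 5.61 |
| .80 | .88, 2 | .877, 2, 3.91 | .847, 2, 4.28 |

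The criterion reproduces all four tabulated medians, and all four probabilities to within .01. The list misses two medians and falls short of every probability by .03 to .06. Adding only 4/5 gives .326/.495/.686/.863 with medians 10/10/5/2. Adding only 6/8 gives .316/.489/.686/.865 with medians 10/10/6/2. Neither addition alone reproduces the table; both together do.

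**Step 4: how often it matters.** The probability that the criterion is first met at 4/5 or 6/8 is 2q⁴(1−q) + 7q⁶(1−q)²:

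- .50: .063 + .027 = .090
- .60: .104 + .052 = .156
- .70: .144 + .074 = .218
- .80: .164 + .073 = .237

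**Step 5: other readings.** Filling the gaps with 5/5 and 7/8 changes nothing, because neither can be reached without an earlier listed stop. Priors beta(1,1) and beta(2,2) do not stop at 2/2. Priors beta(.25,.25), beta(.505,.495) and beta(1,.5) all stop at 4/5 and 6/8. With the stated prior, only a cutoff from .9233 (6/8) up to just below .9244 (2/2) would give the printed list, which contradicts both the stated .90 and the table.

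**The case against.** Five points can be made for the plan.

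- **The criterion governs.** It is stated first and is correct. The list follows as a consequence and does not say that these are the only stopping points, so 4/5 already triggers a stop. Section 9.0 also allows removal for unacceptable toxicity at the study chairman's judgment. This softens the point, but the protocol still gives two answers at 4/5 and 6/8 without saying which prevails, and a discretionary clause does not replace a stopping boundary. That staff would work from the list is an inference; the documents do not say how monitoring is done.
- **The net effect is modest.** This stands. One further toxicity takes 4/5 to 5/6 and 6/8 to 7/9, both listed. At true rates of .60 to .80 that happens with the next patient 60% to 80% of the time, so most affected trials stop one patient late.
- **Look timing is not stated.** With a 6-month window, a sixth patient could be treated before 4/5 is known, whichever version is used. The exact figures do rest on a look after each patient. But the tabulated medians of 5 and 8 require stops at those numbers, so the plan's own table assumes such looks.
- **The table is not an exact match either.** It prints .35 and .70 where exact values round to .34 and .71. Simulation error is possible, but the plan does not say how the table was made. That it came from the criterion is therefore an inference, though a strong one.
- **4/4 and 6/7 are not wrong.** Both meet the criterion. The list may have been meant to give, for each toxicity count, the largest number of patients that still triggers a stop, with 4/4 and 6/7 printed for 4/5 and 6/8. That is plausible but not documented, and the finding does not depend on it.

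**Conclusion.** The concern holds. The list omits 4/5 (.912) and 6/8 (.923), the only points after 2/2 at which the stated criterion can first be met. The criterion and the table agree with each other, and the list is out of line with both.

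Used as printed, the list lowers the early-stopping probability by 3 to 5 percentage points and raises the mean sample size by 0.2 to 0.4 patients. The median rises from 8 to 10 at a true rate of .60 and from 5 to 6 at .70. In 9%, 16%, 22% and 24% of trials, at rates .50 to .80, at least one more patient would be treated after the criterion was first met.

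These figures assume a look after every patient with complete outcomes, independent outcomes at a common rate, and a cap of 10. The posterior values at 4/5 and 6/8 need none of these timing assumptions. The correction is necessary because this is the safety boundary of a 10-patient trial and is wrong as written, not because the average effect is large.

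**What to change.** Reconcile the list with the criterion and the table by adding the two missing points: 2/2, 3/3, 4/4, 4/5, 5/6, 6/7, 6/8, 7/9. Equivalently, give one entry per toxicity count, stated as the largest number of patients that still triggers a stop: 2/2, 3/3, 4/5, 5/6, 6/8, 7/9. Avoid wording such as 7 of 9 or more. At 7/10 the posterior probability is .898, below the threshold, although this has no effect at the cap of 10. Add a short clause saying that the posterior criterion governs if the two ever differ.

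The operating characteristics table can stay. If it is reissued, the exact stopping probabilities at .50 and .70 are .34 and .71.

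The cost is one line of protocol text. The prior, threshold, maximum sample size and design do not change.
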